## 10.3 Study Monitoring

The Sponsor or designee will be responsible for monitoring the study according to GCP and applicable regulations. The study will be monitored by a Clinical Research Associate (CRA) in compliance with GCP, ICH guidelines, and applicable regulations. The investigator will be visited by a CRA prior to the study and at regular intervals during the course of the study. These visits are to verify adherence to the protocol. The CRA will review the ICFs and verify CRF entries by comparing them with the source documents (hospital/clinic/office records) that will be made available for this purpose. The CRA will review the maintenance of regulatory documentation and product accountability. The monitor will review the progress of the study with the investigator and other site personnel on a regular basis. CRFs may be collected during these visits. At the end of the study, a closeout monitoring visit will be performed. Monitoring visits will be arranged with site personnel in advance at a mutually acceptable time. Sufficient time must be allowed by the site personnel for the monitoring of CRFs and relevant source documents. The coordinator and/or investigator should be available to answer questions or resolve data clarifications. Adequate time and space for these visits should be made available by the investigator and study staff.

#### 10.4 Audits and Inspections

During the course of the study and/or after it has been completed, 1 or more sites may be audited by authorized representatives of the Sponsor. The purpose of the audit is to determine whether or not the study is being conducted and monitored in compliance with recognized GCP/ICH guidelines and regulations.

Additionally, the study may be inspected by regulatory authorities. These inspections may take place at any time during or after completion of the study and are based on local regulations.

#### 10.5 Modifications to the Protocol

The procedures defined in the protocol and CRFs will be carefully reviewed to ensure that all parties involved with the study fully understand the protocol. To ensure the validity of the data, no deviations from the protocol (with minimal exceptions) may be made unless the issue is broad enough to warrant revision of the protocol. Such revisions must be submitted to and have documented approval from the Sponsor and IRB prior to implementation. The only circumstance in which an amendment may be initiated without prior IRB approval is to eliminate an apparent immediate hazard to a subject or subjects. In such a case, however, the investigator must notify the Sponsor immediately and the IRB within 5 working days after implementation.

## 10.6 Completion of the Study

The investigator is required to forward CRFs and all other relevant data and records to the Sponsor or designee. The investigator will complete and report (submission of CRFs) his/her study in satisfactory compliance with the protocol as soon as possible after the completion of the study.

The investigator must submit a final report to the IRB and the Sponsor within 1 month of study completion or early termination.

#### 11 CONFIDENTIALITY, USE OF INFORMATION, AND PUBLICATION

All information related to this study that is supplied by the Sponsor and not previously published is considered confidential information. This information includes but is not limited to data, materials (protocol, CRFs), equipment, experience (whether of a scientific, technical, engineering, operational, or commercial nature), designs, specifications, know-how, product uses, processes, formulae, costs, financial data, marketing plans and direct selling systems, customer lists, and technical and commercial information relating to customers or business projections used by the Sponsor in its business. Any data, inventions, or discoveries collected or developed as a result of this study are considered confidential. This confidential information shall remain the sole property of the Sponsor, shall not be disclosed to any unauthorized person or used in any unauthorized manner without written consent of the Sponsor, and shall not be used except in the performance of the study.

The information developed during the course of this study is also considered confidential and will be used by the Sponsor in the development of the study medication. The information may be disclosed as deemed necessary by the Sponsor. To allow the use of the information derived from this study, the investigator is obliged to provide the Sponsor with complete test results and all data developed in the study. The information obtained during this study may be made available to other investigators who are conducting similar studies.

The investigator shall not make any publication related to this study without the express written permission of the Sponsor. If the investigator wants to publish or present the results of this study, he or she agrees to provide the Sponsor with an abstract, manuscript, and/or presentation for review 60 days prior to submission for publication or presentation. The Sponsor retains the right

to delete confidential information and to object to suggested publication/presentation and/or its timing (at the Sponsor's sole discretion).

## 14 APPENDIX 1: FILLER FIRST AID PROTOCOL (CHESTNUT C., 2018)

#### Materials that are needed on-site:

- Hyaluronidase (Hylenex)
- Aspirin 325mg
- Nitroglycerin paste

## Provide the following contacts to subjects and these contacts should also be posted onsite for easy reference:

- Ophthalmologist "on call"
- Closest ER with stroke management capability with directions to ER

## Preparation:

- The above materials should be gathered and labeled for emergency use only (to ensure they are available should an urgent situation arise).
- Staff should be educated regarding the urgent nature of such an event and the location of all materials and contact information.
- Investigators may wish to familiarize themselves with the retrobulbar injection technique via literature or on line training.

It is critical to recognize any intravascular events during injections and act quickly to maximize likelihood of reversal. As soon as an intravascular is recognized, **stop any further injections**.

#### If a skin infarction is identified:

- Apply nitroglycerin paste apply liberally to the affected area and massage in gently, expect headache complaint from subject but do not withhold the treatment.
- Massage area to help promoted blood flow
- Dispense Aspirin 325 mg Have patient chew this or the aspirin may be placed sublingually for maximum rapid absorption
- If blanching persists, consider infiltration with hyaluronidase
  - o Infiltrate in the area where material was being injected this may allow hyaluronidase to enter the same vessel that was inadvertently cannulated.
  - Infiltrate in the area of blanching or ischemia as well
  - o Inject a minimum of 50 units into each area; investigators are free to use larger doses as they see fit.
  - Hyaluronidase may be repeated as needed.
- Hot Packs Towels or gel packs warmed in a microwave can be applied to the area of decreased blood flow.

• Monitor the subject and the area of blanching ischemia. If blanching persists after 24 hours,—consider hyperbaric oxygen treatments.

# If signs/symptoms of visual changes, opthalmoplegia, blindness, ocular pain (usually immediately) occur:

- Dispense Aspirin 325 mg Have patient chew or place the tablet sublingually for maximum rapid absorption
- Massage the globe with repeated inward compression and release this may free any embolic material
- Infiltration with hyaluronidase into area being corrected or augmented
- Have staff call ophthalmology: *Insert physician and cell phone number* or on-call ophthalmology at *nearest center with on-call ophthalmology*, and arrange transport
  - o Bring hyaluronidase with the subject to the ophthalmologist at least 300 units.
- If transport time to ophthalmology or ER is more than 60 minutes, consider performing retrobulbar hyaluronidase administration, 300-600 units at inferior, lateral orbital rim through orbital septum with 1-1.5 inch 27 gauge needle avoiding globe

  After above measures, expedite to emergency room, the retina can tolerate approximately 90 minutes of ischemia until damage becomes permanent.

## If stroke symptoms are recognized:

- Dispense Aspirin 325 mg Have patient chew this or the aspirin may be placed sublingually for maximum rapid absorption
- Infiltration with hyaluronidase into area being corrected or augmented
- Call for transport to ER immediately
- Inform local stroke team during transport

#### 15 APPENDIX 2: PN40082 INSTRUCTIONS FOR USE

PN40082 Injectable Hyaluronic Acid Gel with 0.3% Lidocaine

Caution: Federal Law restricts this device to investigational use. This device is limited by Federal (or United States) law to investigational use

#### DESCRIPTION

PN40082 is a gel of hyaluronic acid generated by Streptococcus species of bacteria, chemically crosslinked with BDDE, stabilized and suspended in phosphate buffered saline at pH=7 with 0.3% lidocaine.

#### **INDICATION**

PN40082 is indicated for submucosal implantation for lip augmentation and dermal implantation for correction of perioral rhytids in patients over the age of 21.

#### CONTRAINDICATIONS

- *PN40082* is contraindicated for patients with severe allergies manifested by a history of anaphylaxis or history or presence of multiple severe allergies.
- *PN40082* contains trace amounts of gram positive bacterial proteins and is contraindicated for patients with a history of allergies to such material.
- *PN40082* is contraindicated for patients with bleeding disorders.
- *PN40082* is contraindicated for implantation in anatomical spaces other than the dermis or submucosal implantation for lip augmentation.
- *PN40082* should not be used in patients with previous hypersensitivity to local anesthetics of the amide type, such as lidocaine.

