#### 7.3.2 Exclusion Criteria

Subjects who meet any of the following criteria will be excluded from the study:

- 1. Women who are pregnant, lactating, or planning a pregnancy.
- 2. Subjects with a known history of allergy, anaphylaxis or hypersensitivity to injectable hyaluronic acid products, local anesthetics of the amide type such as lidocaine, or to latex.
- 3. Subjects with a significant ongoing adverse event from PRO 2018-02 or PRO 2018-03 that in the opinion of the investigator could be worsened by participation in this study.
- 4. Subjects that experienced an SAE, AESI, visual changes or other serious medical conditions during PRO 2018-02 or PRO 2018-03.
- 5. Subjects with abnormal vision evaluations (Confrontational Visual Fields, Ocular Motility) or abnormal Snellen Visual Acuity at Visit 1 pre-treatment as defined in section 7.6.5 and Appendix 5.
- 6. Subjects who are unable to withhold thrombolytics, or inhibitors of platelet aggregation or nonsteroidal anti-inflammatory drugs (NSAIDs, e.g., aspirin, ibuprofen) or other substances known to increase coagulation time (e.g., herbal supplements with garlic or gingko) within 10 days before AND after any injection session.
- 7. Subjects with clinically significant organic disease including clinically significant cardiovascular, hepatic, pulmonary, neurologic, or renal disease or other medical condition, serious intercurrent illness, or extenuating circumstance that, in the opinion of the investigator, preclude participation in the trial.
- 8. Subjects with lip tattoos, piercings, facial hair, or scars that would interfere with visualization of the lips and perioral area for the effectiveness assessments.
- 9. Subjects with abnormal lip function, with inability to effectively sip water through a straw.
- 10. Subjects with abnormal lip sensation with inability to feel a 0.4G monofilament or a cotton wisp at any site on the lip.
- 11. Subjects with moderate or severe abnormal lip asymmetry.

- 12. Subjects with any mass formation on the lip.
- 13. Subjects with dentures or any device covering all or part of the upper palate, and/or severe malocclusion or dentofacial or maxillofacial deformities as judged by the Treating Investigator. Subjects planning to undergo extensive dental procedures such as dental implants, multiple tooth extractions, or oral surgery should not participate. Minor dental procedures such as teeth cleaning and repair of caries are not exclusionary.

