- 14. Subjects that have undergone facial plastic surgery or received permanent facial implants (e.g., polymethylmethacrylate, silicone, polytetrafluoroethylene, polyacrylamide, lifting threads) anywhere in the face or neck, or are planning to be implanted with any of these products during the study.
- 15. Subjects that have undergone semi-permanent dermal filler treatment (e.g., calcium hydroxylapatite, poly-L-lactic acid) in the lower face (below the orbital rim) within 12 months before enrollment or are planning to undergo such treatment during the study.
- 16. Subjects that have undergone facial tissue augmentation with fat injections, botulinum toxin injections in the lower face (below the orbital rim), mesotherapy, or cosmetic procedures in the face or neck (e.g., face-lift, laser, photo-modulation, intense pulsed light, radio frequency, dermabrasion, moderate or greater depth chemical peel, microneedling, or other ablative procedures) within 9 months before enrollment or are planning to undergo any of these procedures during the study.
- 17. that have used ANY lip filling agents within 12 months of study enrollment (hyaluronic acid products, collagen-based products, etc.) other than Investigational Device administered in PRO 2018-02 and PRO-2018-03.
- 18. Subjects that have used any lip plumping products or devices within 10 days before enrollment or are planning to use such products during the study.
- 19. Subjects that have begun using any over-the-counter (OTC) or prescription oral or topical anti-wrinkle products for the lips or around the mouth within 90 days before enrollment or are planning to begin using such products during the study (Subjects who have been on a stable regimen of such products for at least 90 days are eligible for the study and must continue their regimen throughout the study).
- 20. Subjects that have a history or presence of bleeding disorders.
- 21. Subjects that have used systemic corticosteroids or immunosuppressive medications within 30 days prior to treatment.
- 22. Subjects that are on a concurrent regimen of lidocaine or structurally related local anesthetics (e.g., bupivacaine)
- 23. Subjects that have an active inflammation (skin eruptions such as cysts, pimples, rashes, or hives), infection cancerous or precancerous lesion, or unhealed wound on the face.
- 24. Subjects that have a history of known susceptibility to keloid formation or hypertrophic scars.
- 25. Subjects that have porphyria.

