#### 7.4.2 Randomization

Subjects who satisfy all of the eligibility criterial will be randomized in a 1:1:1 ratio to treatment with RV001, RV001 with a topical anesthetic or PN40082. Randomization will be performed according to a computer-generated randomization scheme that will be generated and maintained by an independent third party. A sealed copy of the randomization scheme should be retained at each site and should be available to regulatory authorities at the time of site inspection to allow for verification of the treatment identity for each subject. A unique randomization subject number will be assigned to each subject in ascending order. Each site will receive the randomization scheme.

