## 7.6.3 Significant Medical History/Demographic Information

Medical history and demographic information will be updated if/as needed at Visit 1/Day 1 to record any changes since Visit 1 in Protocol PRO 2018-02.

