#### **PRECAUTIONS**

- PN40082 is packaged for single use. Do not resterilize. Do not use if package is opened or damaged.
- The safety or effectiveness of *PN40082* for the treatment of anatomic regions other than lips or perioral rhytids has not been established in controlled clinical studies.
- As with all transcutaneous procedures, *PN40082* implantation carries a risk of infection. Standard precautions associated with injectable materials should be followed.
- The safety of PN40082 for use during pregnancy, in breastfeeding females or in patients under 22 years has not been established, and these individuals are excluded from this study.
- Subjects with known susceptibility to keloid formation are excluded from this study.
   Formation of keloids may occur after dermal filler injections.
- Hyperpigmentation may occur after dermal filler injections. Subjects with known hyperpigmentation are excluded from this study.
- PN40082 should be used with caution in patients on immunosuppressive therapy.
- Bruising or bleeding may occur at PN40082 injection sites. Patients who have undergone
  therapy with thrombolytics, anticoagulants, or inhibitors of platelet aggregation in the 3
  weeks preceding treatment with PN40082 have not been studied.
- After use, syringes and needles should be handled as potential biohazards. Disposal should be in accordance with accepted medical practice and applicable local, state and federal requirements.
- The safety of PN40082 with concomitant dermal therapies such as epilation, UV irradiation, or laser, mechanical or chemical peeling procedures has not been evaluated in controlled clinical trials.
- Patients should minimize exposure of the treated area to excessive sun, UV lamp exposure and extreme cold weather at least until any initial swelling and redness has resolved.
- If laser treatment, chemical peeling or any other procedure based on active dermal response is considered after treatment with *PN40082*, there is a possible risk of eliciting an inflammatory reaction at the implant site. This also applies if *PN40082* is administered before the skin has healed completely after such a procedure.

• Injection of *PN40082* into patients with a history of previous herpetic eruption may be associated with reactivation of the herpes.

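### Two allergy contraindications in both instructions for use are not fully covered by the exclusion criteria, so a subject can be eligible yet contraindicated in all three arms.

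*Combined protocol and SAP*

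**What the plan says.** The Contraindications part of Appendix 2 (PN40082) states that the device is "contraindicated for patients with severe allergies manifested by a history of anaphylaxis or history or presence of multiple severe allergies". It adds that the gel "contains trace amounts of gram positive bacterial proteins and is contraindicated for patients with a history of allergies to such material". Appendix 3 says the same of RV001 on both points. Each Description section gives the source of the product as a "gel of hyaluronic acid generated by Streptococcus species of bacteria".

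The only allergy criterion is exclusion 2, worded identically in the synopsis and in Section 7.3.2. It excludes a "known history of allergy, anaphylaxis or hypersensitivity to injectable hyaluronic acid products, local anesthetics of the amide type such as lidocaine, or to latex". Another contraindication, bleeding disorders, has its own criterion, exclusion 20: "Subjects that have a history or presence of bleeding disorders".

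Section 7.4.2 makes the listed criteria the gate to treatment: "Subjects who satisfy all of the eligibility criterial will be randomized in a 1:1:1 ratio". Under Section 7.6.3 the medical history is "updated if/as needed at Visit 1/Day 1 to record any changes since Visit 1 in Protocol PRO 2018-02".

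The Precautions lists in both appendices also state: "Subjects with known hyperpigmentation are excluded from this study".

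**The concern.** The contraindications are wider than the criteria meant to enforce them. The severe-allergy contraindication names no allergen, while exclusion 2 names three classes. Someone with a history of anaphylaxis from another cause, with several severe allergies to other substances, or with a known allergy to gram-positive bacterial protein can pass the list in Section 7.3.2 and receive an elective cosmetic injection that the product's own instructions advise against for that person.

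Randomization does not reduce the exposure. All three arms receive PN40082 or RV001, and both carry the same contraindications. What is at stake is subject safety, and the sponsor's ability to show that the device was used within its own instructions. Nothing here suggests that the pain scores or adverse event rates would differ between arms because of it.

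**Working it through.** The plan gives no figure on this point, so the check is a line-by-line comparison of Appendices 2 and 3 with inclusion criteria 1 to 5 and exclusion criteria 1 to 29.

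**Contraindications.** Each appendix lists five. One concerns the site of implantation, which leaves 5 − 1 = 4 that describe the patient:

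| Contraindication (both appendices) | Criterion in Section 7.3.2 | Match |
|---|---|---|
| Severe allergy: any anaphylaxis, or multiple severe allergies | Exclusion 2, for three allergen classes only | Partial |
| Allergy to gram-positive bacterial proteins | None by name | Not named |
| Bleeding disorders | Exclusion 20 | Full |
| Hypersensitivity to amide anesthetics (for RV001, when used with a topical anesthetic) | Exclusion 2 | Full |

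Two are matched, one is partly matched and one is not named, so two need attention.

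**Could another criterion catch these subjects?**
- Exclusion 4 covers serious events during PRO 2018-02 or PRO 2018-03. It does not reach earlier history. For subjects who skipped PRO 2018-03, it also misses events after PRO 2018-02 ended.
- Exclusion 7 allows exclusion for another medical condition, but only on the investigator's opinion, and it does not mention allergy.
- Exclusion 5 refers to Appendix 5, so the protocol does bring an appendix into eligibility when it intends to. No criterion refers to Appendix 2 or 3. Section 7.9.6.3 cites them only for judging whether an adverse event is expected.
- The Visit 1 history update may record a new anaphylaxis, but no criterion makes that entry disqualifying.

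**Could exclusion 2 be read more widely?** Only if anaphylaxis stands alone, detached from the listed products. Allergy would then stand alone too, and anyone with any allergy would be excluded. That cannot be the intent.

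**Example.** A subject completed PRO 2018-02, skipped PRO 2018-03, and has a history of venom anaphylaxis. No exclusion names this history. Whichever arm is drawn, the device is contraindicated.

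**Statements that a group is excluded from the study.** Each Precautions list has three:
- Pregnancy, breastfeeding or age under 22: matched by inclusion 2 and exclusion 1.
- Keloid susceptibility: matched by exclusion 24.
- Known hyperpigmentation: matched by none of the 29 exclusions.

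**Lines to reconcile.** 2 contraindications + 1 precaution = 3 per appendix, and 3 × 2 = 6 over both. Of these, 2 × 2 = 4 are contraindications. Because the two appendices repeat each other, there are three distinct items.

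**The case against.** The best defence is that Section 7.3.2 is not the only control. The appendices are part of the protocol. The Treating Investigator is a board-certified dermatologist or plastic surgeon who must follow the protocol and other study instructions (Section 7.6.1), and exclusion 7 lets an investigator turn such a subject away. This is also a roll-over study. Every subject has already had a filler under PRO 2018-02, a serious allergic event in either earlier study would normally trigger exclusion 4, and for those coming from PRO 2018-03 Visit 1 falls within 14 days of that study's Month 6 call. Those subjects have already received PN40082, bacterial proteins included, and a known reaction to an injectable hyaluronic acid product is excluded anyway.

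Much of this stands as mitigation. An attentive investigator may well decline such a subject, prior exposure may lower the risk, and the group with a bacterial-protein allergy and no reaction to a filler is probably small. It does not close the gap. A labelled contraindication should not depend on discretion under a clause that does not mention allergy, and the instructions make no exception for prior tolerance. Prior tolerance is also incomplete. A subject given Restylane Silk in PRO 2018-02 who did not enter PRO 2018-03 is eligible and need not have received the sponsor's gel in those studies. The earlier protocols may have screened for these histories, but their criteria are not in the documents and this protocol does not import them.

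It is also fair to say that hyperpigmentation is a separate inconsistency, and that counting six lines makes three distinct items look like more.

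**Conclusion.** The concern holds. Two of the four patient-level contraindications in each appendix are not fully covered by the eligibility criteria, and the gap applies in three of three arms. The conclusion rests on the natural reading of exclusion 2, in which its allergy terms attach to the three named product classes, and on treating investigator discretion as no substitute for a stated criterion.

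The number of contraindicated subjects who would enter cannot be estimated from the documents. It may be small, and total enrolment is expected to be below the 158 enrolled in PRO 2018-02. The mismatch itself is certain from the text. The risk it adds is less certain, because screening in the earlier studies cannot be seen. Sample size and the comparisons between arms are not called into question. The correction should be made because it is cheap and concerns safety. The hyperpigmentation mismatch is real but secondary: it is a precaution, and the conclusion does not depend on it.

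**What to change.** Extend exclusion 2, in both the synopsis and Section 7.3.2, so that it also excludes:
- any history of anaphylaxis, whatever the cause;
- a history or presence of multiple severe allergies;
- known allergy to gram-positive bacterial proteins.

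Make this an explicit check in the Visit 1 eligibility review, covering lifetime history and not only changes since PRO 2018-02.

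For hyperpigmentation, either add an exclusion or delete the sentence from Appendices 2 and 3. The sponsor's medical team should decide which.

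The cost is a wording change in the synopsis, Section 7.3.2 and possibly the two appendices, IRB approval of that change (Section 10.5), and perhaps a few more screen failures.
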